6 STUDY ASSESSMENTS

The Study Flowsheet (time and events table) provided below lists the study activities throughout the protocol.

STUDY FLOW CHART			
		Washo	

	Screen (Office Visit)	First Arm (Treximet™ or Usual Triptan) - Treat 3 Migraines			ut Windo w (at least 48h post V4 tx) (Office Visit)	Second Arm (Treximet™ or Usual Triptan) - Treat 3 Migraines			EOS (Office Visit)
Procedure	Visit 1	Visit 2	Visit 3	Visit 4	Visit 5	Visit 6	Visit 7	Visit 8	Visit 9
Informed Consent	X								
Inclusion/Exclusion	X								
Office Visit (PE, Vitals Neuro Exam)	X								X
Urine Pregnancy Test (if female and childbearing potential)	X				X				X
Conmeds	X				X				X
AE/SAE collect					X				X
Migraine History & update	X				X				
Medical History- & update	X				X				X
Educ/Disp/Revu Diary	X	X	X	X	Collect	x	x	x	Collect
Randomization	X				Switch TX Arm				
Disp/Take/Collect Study Drug	X	X	X	X	Collect	X	X	X	Collect
WPAI		X	X	X	Collect	X	X	X	Collect
CORS 1				X	Collect			X	Collect
CORS 2								X	Collect
MigraineAct	X			X	Collect			X	Collect
KP Data	X				X				X

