3 INVESTIGATIONAL PLAN

3.1 SUMMARY OF STUDY DESIGN

This is a single site, randomized, open-label, two arm, crossover, study of subject productivity improvement and satisfaction with migraine treatment using Treximet™ vs usual triptan.

This study will recruit 60 patients who are employed in a paying job, who have episodic migraine (<15 days/month), who are using acute care triptan monotherapy for their migraine (excluding combinations of any sort, such as acetaminophen [APAP] and non-steroidals [NSAIDs]) and who have no contraindications to triptan or NSAID use.

In one arm of the study, patients will treat 3 work day migraines with their usual triptan and in the other arm of the study the same patients will treat 3 work day migraines with Treximet. The medication that they use in the first arm of the study is determined by randomization. They will maintain headache diaries for the duration of the study and fill out the WPAI after each work day migraine. After treating 3 work day migraines, they will also fill out CORS Part 1 and Migraine-ACT.

Between the completion of the 3rd migraine attack treatment, and the start of the second treatment arm, there will be a minimum of a 48 hour washout period and an office visit.

In the second arm, after cross over to the other treatment, the sixty patients will maintain headache diaries, treat 3 attacks during any day in which they are scheduled to work, and fill out the WPAI after each attack. Additionally, after 3 attacks are treated, they will fill out CORS Part 1, CORS Part 2 and Migraine-ACT. This second arm differs from arm one in that the subjects will treat their migraines with the other medication from that assigned in the first arm.

Subject participation will last approximately 3 months, depending on the days needed to treat migraines during the workday according to protocol.

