11. subjects with a history of significant ischemic cardiac symptoms (to include angina pectoris of any type; silent myocardial ischemia; cerebrovascular disease (including any type of stroke, transient ischemic attack), or peripheral vascular disease; such as ischemic bowel disease; coronary artery bypass graft surgery)
12. subjects with uncontrolled hypertension
13. subjects with use of monoamine oxidase-A inhibitors
14. subjects with current use of ergotamine-containing or ergot-type medications, like DHE
15. subjects using 5-HT agonists
16. subjects with diagnosis of basilar or hemiplegic migraines
17. subjects with allergy to naproxen
18. subjects who are allergic to aspirin or NSAIDS where such allergies induce syndrome of asthma, nasal polyps, urticaria and hypotension

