6.2 SAFETY

Adverse events will be collected via subject report on study diaries and at office visits during the physician assessments and noted in the electronic medical record. Adverse events will be noted from the date of the first study visit until the end of study visit has been completed.

Serious Adverse Events will be reported to the Cleveland Clinic Office of the IRB, to Pernix Therapeutics and the FDA, in accordance with IRB policy. Medical details of these Serious Adverse Events will be noted in the electronic medical record.

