5.7 Hypertension

Significant elevation in blood pressure, including hypertensive crisis with acute impairment of organ systems, has been reported on rare occasions in patients treated with 5-HT₁ agonists, including patients without a history of hypertension.

NSAIDs, including naproxen, a component of TREXIMET, can lead to onset of new hypertension or worsening of preexisting hypertension, either of which may contribute to the increased incidence of cardiovascular events. Patients taking thiazides or loop diuretics may have impaired response to these therapies when taking NSAIDs.

Monitor blood pressure in patients treated with TREXIMET. TREXIMET is contraindicated in patients with uncontrolled hypertension [*see Contraindications (4)*].

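### Vitals are scheduled at Visits 1 and 9 but not at the Visit 5 crossover, so no patient is scheduled for a blood pressure reading at both office visits around the Treximet period (minor safety point)

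*Combined protocol and SAP*

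**What the plan says.** The study flow chart (section 6) is presented as the list of study activities. Its only row with vitals is "Office Visit (PE, Vitals Neuro Exam"), marked at Visit 1 (screening) and Visit 9 (end of study). The inclusion/exclusion row is marked at Visit 1 only.

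Visit 5 is an in-person visit. Section 3.1 states that between the two periods "there will be a minimum of a 48 hour washout period and an office visit", and the flow chart places the treatment switch there. The procedures marked at Visit 5 include "Urine Pregnancy Test (if female and childbearing potential"), concomitant medications, adverse events, and updates of migraine and medical history. Vitals are not among them. Section 6.2 says that adverse events are collected on diaries and "at office visits during the physician assessments"; it names no blood pressure measurement.

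Exclusion 12 in section 4.3 is "subjects with uncontrolled hypertension". The label in Appendix 11.6, section 5.7, instructs: "Monitor blood pressure in patients treated with TREXIMET. TREXIMET is contraindicated in patients with uncontrolled hypertension". The same section warns that NSAIDs, including naproxen, "can lead to onset of new hypertension or worsening of preexisting hypertension".

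**The concern.** Visit 5 is the one office visit that touches the Treximet period in both sequences: it comes just before Treximet for triptan-first patients and just after it for Treximet-first patients. Leaving vitals out there has a different consequence in each sequence.

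- **Triptan-first.** These patients begin Treximet after Visit 5 with no scheduled blood pressure since screening, so exclusion 12 and the matching label contraindication are not checked against a current reading. This is a missing check before a new drug. Their triptan use is unchanged from entry and they have had no study naproxen, so nothing points to a study-drug effect by that time.
- **Treximet-first.** These patients have finished Treximet by Visit 5, and the label's advice to monitor, and its NSAID warning, apply to them. Their next scheduled reading comes only after the whole triptan period.

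What could be missed is an undiagnosed, symptom-free rise before Treximet in the first group, or found later than necessary in the second.

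**Working it through.** **Inputs**
- Vitals visits: 1 and 9 (flow chart, section 6).
- Sequences: 30 Treximet-first and 30 triptan-first (counted from the 60 rows of Appendix 11.7).
- Naproxen half-life about 19 h; sumatriptan about 2 h (label section 12.3).
- Washout at least 48 h, with no maximum (section 3.1).
- Power assumptions: difference 1 point, SD of the within-patient difference 2.5, 30 per sequence, stated power 86% (section 4.1); alpha 0.05 (section 8.2), taken as two-sided.

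**Step 1. Scheduled readings around Treximet**

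| Sequence | n | Office visit before Treximet | Office visit after Treximet | Both |
|---|---|---|---|---|
| Treximet-first | 30 | Visit 1: yes | Visit 5: no | 0 |
| Triptan-first | 30 | Visit 5: no | Visit 9: yes | 0 |
| Total | 60 | 30 | 30 | 0 |

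With vitals at Visit 5 the last column becomes 30 + 30 = 60, if all patients complete.

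**Step 2. How long Treximet-first patients wait for a reading**

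Section 3.1 says "Subject participation will last approximately 3 months". Taking 3 months as 13 weeks and splitting it evenly between the periods (an assumption), Visit 9 falls 13/2 = 6.5 weeks after Visit 5. If the second period takes one third to two thirds of the time, the gap is 13/3 = 4.3 to 26/3 = 8.7 weeks.

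Visit 5 can fall much closer to exposure. At the 48 h minimum, 48/19 = 2.5 naproxen half-lives have passed and 0.5^(48/19) = 17% remains. That is the most favourable case: at 96 h, 0.5^(96/19) = 3% remains. Sumatriptan is already 48/2 = 24 half-lives past at 48 h.

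**Step 3. What withholding Treximet at Visit 5 could cost in power**

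For a period-adjusted crossover comparison with n1 and n2 patients per sequence,

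SE = sqrt[(2.5²/4) × (1/n1 + 1/n2)],

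and power comes from the noncentral t distribution with n1 + n2 − 2 degrees of freedom and noncentrality 1/SE.

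With 30/30: SE = sqrt(1.5625 × 0.06667) = 0.3227, noncentrality 3.098, power 86.1%. This reproduces the plan's 86%.

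| Triptan-first / Treximet-first with both periods | Power |
|---|---|
| 30 / 30 | 86.1% |
| 29 / 30 | 85.5% |
| 28 / 30 | 84.9% |
| 27 / 30 | 84.2% |

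The losses of 1, 2 and 3 are illustrative. The documents give no rate of uncontrolled blood pressure, so neither the number withheld nor a probability of detection can be forecast.

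**The case against.** **The blank may be a slip.** The row name joins the office visit with vitals, Visit 5 is headed as an office visit, and section 6.2 speaks of physician assessments at such visits. An omitted X is plausible. However, Visits 1 and 9 carry the same heading and still have their own X, so the heading alone does not schedule vitals at Visit 5. A reader might infer that no patient will have a blood pressure taken there. The documents support only that none is scheduled; a reading could be taken in practice.

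**Visit 5 is not free of safety checks.** A reader might infer that only pregnancy is rechecked. In fact the medication and history updates bear on several other exclusions, hypertension included, and with adverse event collection they would pick up known or symptomatic cases. This stands, and it narrows the gap to rises that are undiagnosed and symptom-free.

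**A Visit 5 reading adds limited information after Treximet.** A lasting rise would still show at Visit 9, and a brief one may be gone by 48 h. This also stands. What Visit 5 adds for Treximet-first patients is earlier detection, or detection of a rise that resolves before Visit 9. It could not attribute the rise to a drug.

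**No text demands it.** The label sets no monitoring interval, and neither document asks for readings on both sides of Treximet. Exposure is three attacks with at most two tablets each (section 5.2), and label section 12.2 reports no rise over 6 months of intermittent use in 122 normotensive adults. All of this argues for a low rating. The label finding does not cover people with controlled hypertension, whom exclusion 12 allows in.

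**Withholding is discretionary, open-label and confined to one sequence.** The protocol gives no threshold for uncontrolled hypertension, so a Visit 5 decision could remove second-period data selectively. This is a fair caution, met in part by applying the screening standard and reporting the number withheld by sequence.

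**Conclusion.** The point holds as a minor safety improvement. As written, 0 of 60 patients are scheduled for a reading at both office visits around Treximet. The 30 triptan-first patients lack a current reading before starting it, and the 30 Treximet-first patients lack one after it until Visit 9. That is roughly 4 to 9 weeks after Visit 5, depending on how the study time divides.

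This rests on three assumptions: that vitals include blood pressure, that the blank cell means not scheduled, and, for the weeks only, the assumed split of 13 weeks. If vitals do not include blood pressure, the plan schedules none at all, and the same fix applies.

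A reader might take this as evidence of an unsafe design or of a threat to the results. The documents support neither. No aim, endpoint or analysis uses blood pressure, every completer has vitals at the start and end of the study, and the sample-size figure is unaffected.

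**What to change.** Split the flow-chart row into two: vitals including blood pressure at Visits 1, 5 and 9, and physical and neurological examination at Visits 1 and 9 as now. Add a short rule for Visit 5:

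- Measure blood pressure before second-period drug is started.
- For a patient about to start Treximet, repeat an elevated reading and have the study physician apply exclusion 12 by the same standard used at screening. If it is met, withhold Treximet and keep the first-period data.
- For a patient who has finished Treximet, treat the reading as safety monitoring and follow up an elevated value clinically.
- Report the number withheld by sequence, and list vitals by visit descriptively only.

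If the blank was an omitted X, restoring it and adding the rule achieves the same thing.

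The cost is a few minutes per patient at a visit that already takes place. The downside is an occasional loss of second-period data in the triptan-first sequence only, in a plan with no stated allowance for attrition. Losing up to three such patients would lower power from 86.1% to 84.2% on the plan's own assumptions.

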6.1 EFFICACY

Efficacy comparisons of Treximet™ vs Usual Triptan treatment will be collected using the CORS 1, CORS 2, WPAI and Migraine-Act assessment tools. Pain level at time of dose is captured as part of the Study Diary.

6.2 SAFETY

Adverse events will be collected via subject report on study diaries and at office visits during the physician assessments and noted in the electronic medical record. Adverse events will be noted from the date of the first study visit until the end of study visit has been completed.

Serious Adverse Events will be reported to the Cleveland Clinic Office of the IRB, to Pernix Therapeutics and the FDA, in accordance with IRB policy. Medical details of these Serious Adverse Events will be noted in the electronic medical record.

7 DATA MANAGEMENT

Study data points will be collected on the questionnaires and diaries completed by the subjects. These data will be provided to QHS for statistical analysis and to Pernix Therapeutics for their review and analysis.

8 DATA ANALYSIS

8.1 HYPOTHESIS

Treximet™, because of its multiple mechanisms of action and resultant synergy of effects, should be more effective than usual care in improving productivity, reducing migraine impact, and providing patients with optimal treatment upon which they can rely, the latter specifically because of Treximet™'s consistency of response and high pain free and sustained relief efficacy.

8.2 DESIGN AND DATA ANALYSIS CONSIDERATIONS

For the crossover design, there is a special need to identify if a carryover effect exists. For the primary outcome, WPAI score after last attack, the mean sequence sums will be compared with a 2-sample t-test (see Toutenburg in references pp. 344-346). If no significance is found, then the assumption will be that there is no carryover effect and treatment differences will be evaluated through a mixed model analysis. The model will include trial period, sequence (usual triptan f/b Treximet or Treximet f/b usual triptan) and treatment as fixed effects. If carryover does exist, then only the first trial period results will be used and a 2-sample t-test will be conducted to look for treatment differences. A sensitivity analysis will be performed in which WPAI scores from all 3 attacks will be included in the model. A second model will be created with the inclusion of an interaction term between treatment and pain level at time of dose.

Lost Workplace Productivity and Non-Work Activity Time - WPAI analysis

Subjects are to record the number of hours they miss from work due to migraine symptoms (WM), the number of hours they miss from routine activities outside of paid work due to migraine symptoms (RAM), the number of hours they continue to work while having migraine symptoms (WS), the number of hours they continue routine activities while having migraine symptoms (RAS), and how effective they are while continuing routine activities while having migraine symptoms (RAE). Lost workplace productivity (LWP) and lost activity time (LAT)

will be calculated as follows. The overall lost workplace productivity and activity time for the attack will be the sum of the two measures (LWP + LAT) where

$$LWP = WM + (WS \times [(100\% - WE)/100\%])$$

$$LAT = (RAM + (RAS \times [(100\% - RAE)/100\%]))$$

If the subject has indicated that work was not scheduled on a given diary, the LWP for that diary day will be 0 regardless of what information may have been filled out on the diary regarding WM, WS, or WE.

For the secondary outcome Migraine-ACT, a binary outcome will be calculated (e.g. 0=if Migraine-ACT is not favorable, 1=if Migraine-ACT is favorable) and used to identify carryover. [Note: A favorable response in Migraine-ACT is a value of 3 or 4.] The odds of a favorable triptan f/b Treximet sequence will be compared to the odds of a favorable Treximet f/b triptan sequence through an odds ratio, which will be evaluated with a chi-square test (see Toutenburg¹ p. 369). If no significance is found, then the assumption will be that there is no carryover effect. That assumption will be applied when analyzing both the binary and ordinal (levels > 2) values of Migraine-ACT. Treatment differences will be evaluated through a generalized estimating equation with a logit link function (or cumulative logit link function). The models will include trial period, sequence, and treatment as fixed effects. If carryover does exist, then only first trial period results will be used. In that case, treatment differences will be evaluated through a chi-squared test for binary outcomes and through a Mann-Whitney U-test for ordinal outcomes (levels > 2).

All tests for significance will be conducted at the 95% confidence level (i.e. $\alpha = .05$). Analysis will be conducted in SAS® v9.2.

CORS data will be tabulated as follows: For CORS part 1, a frequency count and percent by question answer will be provided. This will be reported by treatment (Treximet™ vs triptan) within period and in total. For CORS part 2, a frequency count and percent will be provided by answer for each question. In addition, a de-identified data set containing CORS information will be provided to Pernix Therapeutics for additional psychometric analysis.

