4. SUBJECT SELECTION

4.1 NUMBER OF SUBJECTS

This study will enroll 60 subjects for participation. There are no other sites for this study.

The sample size was chosen to be a sufficient number to assess the effect of Treximet on the WPAI using a crossover design in which patients will serve as their own controls.

Based on previous GSK studies on Treximet utilizing the WPAI, the effect size between Treximet and usual triptan care is expected to be small. In those studies, comparisons of Treximet to placebo yielded differences of 0.4 to 1.4. For this study, a one-point WPAI difference between Treximet and triptan is assumed to be clinically meaningful. Furthermore, the GSK Treximet studies were parallel designs with standard deviations ranging from 2.5 to 3.5. To account for the correlation from patients acting as their own controls in this crossover design, a standard deviation of the difference equal to 2.5 is assumed. Under these assumptions, a total sample of 60, with 30 in each sequence, would power the study at 86%.

4.2 INCLUSION CRITERIA:

A subject will be eligible to participate in this study if all of the following criteria apply:

1. subject is 18 years or older at screening
2. subject has a history of migraine greater than 1 year
3. subject has been diagnosed with migraine before age 50
4. subject is an employed person (is paid wages for his/her work)

5. subject has diagnosis of episodic migraine, by IHS criteria
6. subject uses triptan monotherapy as the primary migraine abortive treatment
7. subject is not pregnant or nursing

4.3 EXCLUSION CRITERIA:

A subject will not be eligible to participate in this study if any of the following criteria apply:

1. subject is less than 18 years of age at screening
2. subject does not have history of migraine greater than 1 year
3. subject was diagnosed with migraine after age 50
4. subject is not currently employed
5. subject does not have diagnosis of episodic migraine
6. subject does not use triptan monotherapy as primary migraine abortive treatment
7. subject is pregnant or nursing
8. subjects with a history of stroke, myocardial infarction (including vasospastic coronary artery disease [CAD] or cardiovascular thrombotic events)
9. subjects with gastrointestinal disease history to include ulcers, bleeding or perforations of the stomach or intestines
10. subjects with a history of significant renal or hepatic disease.

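### Section 8.2 assumes no carryover whenever a 0.05 test is not significant, but at 30 per sequence the WPAI test misses a 1-point carryover 86–91% of the time

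*Combined protocol and SAP*

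**What the plan says.** Section 8.2 recognises that a crossover needs attention to carryover. For the primary outcome, the WPAI score after the last attack, "the mean sequence sums will be compared with a 2-sample t-test". The next step depends on that result: "If no significance is found, then the assumption will be that there is no carryover effect and treatment differences will be evaluated through a mixed"-effects model with period, sequence and treatment. On the other branch the plan drops half the data: "and treatment as fixed effects. If carryover does exist, then only the first trial period results will be used", analysed by a two-sample t-test. The level is common to all tests: "All tests for significance will be conducted at the 95% confidence level".

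Migraine-ACT follows the same two-stage logic, with a chi-square test on a dichotomised score. A non-significant binary result then also covers the ordinal analysis: "That assumption will be applied when analyzing both the binary and ordinal (levels > 2) values of Migraine-ACT".

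The plan gives no power for the carryover test, no margin or confidence bound for carryover, and no stated reason to expect carryover to be small. The one WPAI sensitivity analysis adds the scores from all three attacks, which does not address carryover.

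**The concern.** A non-significant test supports an assumption of no carryover only if the test would probably have detected a carryover that matters. This one compares independent groups of 30 on the sum of two periods. The sum retains the between-patient variation that the crossover was chosen to remove, so the test is far weaker than the treatment comparison it is meant to protect.

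A missed carryover biases the retained estimate. The sequence term in the mixed model does not help: in a two-period, two-sequence design, sequence and carryover are aliased, and the treatment estimate remains the within-patient contrast. Carryover of benefit from Treximet into the later triptan period would hide a real effect. Carryover in the other direction would inflate or create one.

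The two-stage rule also has a cost when there is no carryover, because choosing the analysis by a pretest on the same data raises the type I error.

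**Working it through.** **Inputs.** From Section 4.1: 60 patients, 30 per sequence; "a one-point WPAI difference between Treximet and triptan is assumed to be clinically meaningful"; "the GSK Treximet studies were parallel designs with standard deviations ranging from 2.5 to 3.5"; "a standard deviation of the difference equal to 2.5 is assumed". The randomization table (Appendix 11.7) has 30 in each sequence. Alpha is 0.05 (Section 8.2). The plan does not state sidedness, so two-sided is assumed.

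**The plan's own figure.** The noncentrality is 1/(2.5/√60) = 3.098. Two-sided 0.05 with 58 df gives 86.1% power, which agrees with the stated 86%.

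**Variance of the carryover contrast.** Let s be the single-period SD and ρ the within-patient correlation.
- Var(difference) = 2s²(1 − ρ) = 6.25, so ρ = 1 − 6.25/(2s²).
- SD(sum) = √[2s²(1 + ρ)].
- SE of the contrast = SD(sum) × √(2/30).
- CI half-width = t(0.975, 58 df) × SE, where t = 2.00.

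**Chance of missing a carryover of size L** (noncentral t, 58 df, noncentrality L/SE):

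| s | ρ | SD(sum) | SE | 95% CI half-width | L = 0.5 | L = 1 | L = 2 |
|---|---|---|---|---|---|---|---|
| 2.5 | 0.50 | 4.33 | 1.12 | 2.24 | 92.8% | 85.8% | 57.9% |
| 3.0 | 0.65 | 5.45 | 1.41 | 2.82 | 93.6% | 89.2% | 71.3% |
| 3.5 | 0.74 | 6.54 | 1.69 | 3.38 | 94.0% | 91.0% | 78.6% |

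**Bias.** Take a true treatment difference τ and a carryover L into the period after Treximet. The mean within-patient difference (period 1 minus period 2), apart from the period effect, is τ − L in the Treximet-first sequence and −τ in the other. Half the difference between sequences is (2τ − L)/2 = τ − L/2. With L = 2 the shift is 1 point, the whole assumed effect.

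**The planned two-stage rule.** Simulated with 40,000 trials per case for s = 2.5, 3.0 and 3.5, with carryover in the same direction as the treatment effect:

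| Carryover | Mean shift in crossover estimate | Rejection, no treatment effect | Power, true 1-point effect |
|---|---|---|---|
| 0 | 0 | about 7–8% | about 84% |
| 0.5 | 0.25 | about 14% | about 64% |
| 1 | 0.50 | 31–33% | 38–42% |

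The reference for power loss is 84%, not 86%, because the two-stage rule itself costs about 2 points.

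**The case against.** The strongest objection is that carryover is unlikely here, so a weak test does little harm. For drug carryover on the primary outcome that stands. Section 3.1 requires a washout of at least 48 hours and the package insert (Section 12.3) gives a naproxen half-life of about 19 hours, so about 0.5^(48/19) = 17% remains at the minimum gap. The primary score comes from the third treated attack after the switch, later still. A reader might infer that residual naproxen contaminates the triptan period; for this score the documents point the other way.

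They do not exclude carryover of expectation or rating. Treatment is open label, all patients enter as triptan users, and the WPAI form asks patients to rate their effectiveness against their usual performance. Patients returning to a familiar drug after trying the new one are not placed like those who have not yet switched, and a washout does not remove that.

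The second objection concerns size. A 1-point carryover equals the whole assumed treatment effect, so the 31–33% and 38–42% figures illustrate a large carryover and are not expected consequences. That also stands, and is why the 0.5-point results are shown beside them.

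Three further readings are tempting but unsupported. The plan does not call non-significance proof; it makes an assumption, although the analysis then proceeds in the same way. It specifies no report statement that carryover was tested and not found. No miss rate can be given for Migraine-ACT, because neither the response rates nor the exact form of the test, defined by a textbook page, is in the documents.

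**Conclusion.** The concern holds as a flaw in inference and in the analysis rule. Under the protocol's planning SDs, a non-significant WPAI carryover test is the likely result whether or not carryover is present. With a CI half-width of 2.2–3.4 points, even an observed contrast of zero would leave open a 2-point carryover, enough to cancel or create the whole 1-point effect. For Migraine-ACT the same inference is made, and extended from the binary to the ordinal scale; that part of the point rests on logic, not on a calculated rate.

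The miss rates assume normal data, two-sided 0.05, no dropout (any would raise them) and the Section 4.1 SDs. The bias arises only if carryover exists, and the documents do not show that it does. The inflated type I error of about 7–8% needs no carryover at all.

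**What to change.** In Section 8.2, for both WPAI and Migraine-ACT:

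- Delete the inference from a non-significant test to no carryover, and delete the switch to period-1 data. Removing only the first would leave the fallback with no trigger.
- Name the crossover model (mixed model for WPAI, GEE for Migraine-ACT) as the single primary analysis, whatever the carryover test shows.
- State why little carryover is expected: the washout, the naproxen half-life and, for WPAI, scoring at the last attack.
- Report the between-sequence carryover contrast with its 95% CI, and the period-1 estimate with its CI as a sensitivity analysis. Do not state that carryover is absent because the test is non-significant.
- Report the Migraine-ACT contrast on both the binary and the ordinal scale.

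The cost is SAP wording and a few lines of analysis on data already collected, with no extra patients or visits. Dropping the pretest returns the type I error to 5% when there is no carryover. It does not remove bias if carryover exists, so the trial will usually have to say that carryover was not excluded. The period-1 comparison will be imprecise: with SE = s√(2/30) and 58 df, its power for 1 point is about 19–33%.

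### The carryover pretest that selects the primary WPAI analysis raises its type I error from a nominal 5% to about 7%–8%

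*Combined protocol and SAP*

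**What the plan says.** For the primary outcome (WPAI score after the last attack), section 8.2 sets a two-stage rule.

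- **Stage 1, carryover:** "the mean sequence sums will be compared with a 2-sample t-test".
- **Stage 2, pretest not significant:** carryover is taken to be absent and "treatment differences will be evaluated through a mixed model analysis". On the content of that model: "The model will include trial period, sequence (usual triptan f/b Treximet or Treximet f/b usual triptan) and treatment as fixed effects". No subject effect or within-subject covariance is listed.
- **Stage 2, pretest significant:** "If carryover does exist, then only the first trial period results will be used and a 2-sample t-test will be conducted".

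On the level, the same section says: "All tests for significance will be conducted at the 95% confidence level". No adjustment is given for choosing the analysis from the same data.

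The plan also promises a further model: "A sensitivity analysis will be performed in which WPAI scores from all 3 attacks will be included in the model". It does not say whether that model depends on the pretest.

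The secondary Migraine-ACT outcome follows the same pattern: "If carryover does exist, then only first trial period results will be used".

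**The concern.** The pretest compares sums over both periods, and each sum contains the period-1 score that the fallback test then uses alone. When there is no carryover, the pretest is significant only by chance, typically because one sequence group happens to have high scores. The same imbalance then appears in the period-1 comparison as an apparent treatment difference. The first-period test is therefore run mostly in those trials where it is already likely to be falsely significant, yet it is judged at an unadjusted 0.05.

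This bears on the one comparison the trial is powered for. A treatment claim could come from a branch that the pretest opened by chance, with an exaggerated estimate and weak evidential value.

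**Working it through.** **Inputs.** From section 4.1: 30 subjects per sequence (the table in Appendix 11.7 also counts 30 and 30), planned difference 1 point, single-period SD 2.5 to 3.5, SD of the within-subject difference 2.5, stated power 86%. From section 8.2: alpha 0.05 for every test. Assumed: two-sided tests, equal variances, complete data, normal scores, and a mixed model with a within-subject term.

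**Reproducing the plan's figure.** SE = 2.5/√60 = 0.323. Noncentral t power at a difference of 1 is 86.1% (58 df) or 86.2% (59 df), which matches the stated 86%. A one-sided test would give 92.2%, so two-sided testing is the consistent reading.

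**Correlation implied by the planning SDs.** The plan does not state rho. From SD_d² = 2·SD²·(1 − rho), rho = 1 − 2.5²/(2·SD²).

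**Relation between the tests.** With no carryover and no effect, a subject's sum is uncorrelated with the period difference. Its correlation with the period-1 score is √((1 + rho)/2). Hence

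type I error = 0.95 × 0.05 + 0.05 × P(first-period test significant, given pretest significant).

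| Single-period SD | 2.5 | 3.0 | 3.5 |
|---|---|---|---|
| rho | 0.500 | 0.653 | 0.745 |
| Correlation, pretest and first-period test | 0.866 | 0.909 | 0.934 |
| P(first-period significant, given pretest significant), bivariate normal | 0.533 | 0.611 | 0.667 |
| Two-stage error = 0.0475 + 0.05 × row above | 7.4% | 7.8% | 8.1% |
| Two-stage error, simulated t-tests (400,000 trials) | 7.43% | 7.79% | 8.06% |
| Both-period analysis alone, simulated | 5.02% | 5.01% | 5.01% |

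Across rho from 0 to 0.9 the simulated two-stage error is 6.3% to 8.6%. With skewed data (gamma, mean 2.5 or 4 hours, both assumed) it is 6.9% to 7.7%, against 4.1% to 4.9% for the both-period analysis.

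**Planned 1-point effect, no carryover.** Overall power is about 84% with the pretest and 86% without, so the power cost is small. The trouble lies in the branch itself, which opens by chance in 5% of trials:

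| Single-period SD | 2.5 | 3.0 | 3.5 |
|---|---|---|---|
| Correct-direction rejection, effect 1 | 50.0% | 49.9% | 50.3% |
| Wrong-direction rejection, effect 1 | 0.4% | 1.2% | 2.4% |
| Correct-direction rejection, effect 1 relative to no effect | 1.88 | 1.65 | 1.52 |
| Mean estimate when significant in the correct direction (truth 1) | 2.29 | 2.62 | 2.94 |

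With no effect, the branch rejects about 26% to 33% of the time in each direction. A favourable result there is thus only 1.5 to 1.9 times as likely under the planned effect as under none.

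**True carryover, illustrative sizes.** Size means the carryover difference between sequences in period 2. The both-period treatment estimate is biased by half of it.

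| Scenario | Rejection, both-period model | Rejection, two-stage rule |
|---|---|---|
| Carryover 0.5, no effect | 12% | 14% |
| Carryover 1, no effect | 33% | 31%–33% |
| Carryover 2, no effect | 86% | 52%–70% |
| Carryover 2 cancelling a true effect of 1 | 5% | 20%–32% |

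The pretest detects a 1-point carryover in 14.2% / 10.7% / 9.0% of trials and a 2-point carryover in 42.1% / 28.7% / 21.4% (SD 2.5 / 3.0 / 3.5).

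**The unstated model term.** If the model held only the listed fixed effects with independent errors, the both-period test would have type I error of 0.02% to 0.6% and power of 22% to 62%, and the two-stage error would be 3.1% to 3.3%. The 86% in section 4.1 requires the within-subject term.

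**The case against.** **The plan follows a cited textbook procedure and states 0.05 per test, with no level for the two-stage rule.** True as to wording. The citation supports the test statistic, but it does not make the combined rule hold 5%, and the reader of the primary result will take it as a 5% test.

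**The figure depends on a derived correlation, on normality and on exactly zero carryover.** It does. The inflation nevertheless persists for every rho from 0 to 0.9 and for the skewed data tried, though the skewed range is somewhat lower.

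**Most of the overestimation is ordinary selection on significance in a small comparison.** Largely right. First-period tests significant in the correct direction, with no pretest at all, average about 1.7 / 2.0 / 2.3 points. The pretest adds about 0.6 to 0.7.

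**Dropping the pretest gives up protection.** This is the strongest point. With a 2-point carryover the two-stage rule does better, as the table shows. Treatment is open label (section 5.3.2) and WPAI effectiveness is self-estimated (Appendix 11.1), so expectation effects carried into period 2 cannot be excluded. On drug carryover, the 48-hour minimum in section 3.1 and the 19-hour naproxen half-life in the package insert leave 0.5^(48/19) = 17% of naproxen. The usual triptan varies by subject and its half-life is generally not given. Even so, both rules fail badly at 2 points, are about equal at 1 point, and the two-stage rule is slightly worse at 0.5.

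**The pretest could be kept with a stricter fallback.** Testing the first-period comparison at about 0.2% to 0.3% restores 5%, with power near 83.5%. False rejection under a 2-point carryover is then 50% to 68%, but rejection in the cancelling case falls to 6%–8%. It is a workable second choice that leaves the fallback with little use.

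**Conclusion.** The concern holds. As written, the primary WPAI test has a type I error of 7.4% to 8.1% under the plan's own SDs, roughly one and a half times the nominal 5%, when there is neither carryover nor a treatment effect. This rests on two-sided tests, normal data, equal variances, no dropout, a correlation derived from section 4.1, and a mixed model that accounts for the subject. The loss of power is minor (about 84% against 86%). The harm is the inflated error and the weak, exaggerated results on the first-period branch. The all-attacks sensitivity analysis may supply a both-period result, but it does not restore the level of the primary test. Migraine-ACT has the same structure; no size is claimed for it. This should be corrected.

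**What to change.** In section 8.2:

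- Remove the carryover test as the switch between analyses. Make the both-period mixed model the sole primary analysis of WPAI, whatever the carryover comparison shows.
- Keep period, sequence and treatment in that model and state the within-subject term: a subject random effect or an equivalent covariance structure.
- Report the difference in sequence sums with its 95% confidence interval, and the first-period comparison, as descriptive results beside the primary estimate.
- Keep the all-3-attacks model as the sensitivity analysis and state that it is run regardless of the carryover result.
- As a side matter, make the same structural change for Migraine-ACT: the GEE as its main analysis, with the working correlation stated.

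The cost is a change of wording, with no new data, visits or subjects. Because section 8.2 belongs to the combined protocol, it does amend the protocol's primary analysis. The statistical price is the loss of a formal switch if carryover is large, which is why the carryover estimate and its interval should appear with the primary result.
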